#### 8.4 FDA DEFINED VALVULOPATHY AND PULMONARY ARTERIAL PRESSURE

The aortic and mitral valve regurgitation will be categorized as absent, trace, mild, moderate or severe. FDA-defined valvulopathy, or simply "FDA valvulopathy," stipulate that significant valvular regurgitation comprises **mild or greater aortic valve regurgitation and/or moderate or greater mitral valve regurgitation**. The ECHO sub-study data presents the mitral and aortic valve severity as 5 categories; ABSENT, TRACE, MILD, MODERATE, and SEVERE.

For each subject and visit a dichotomous variable will be created, where;

1 = mild or greater aortic valve regurgitation and/or moderate or greater mitral valve regurgitation

0 = aortic valve regurgitation is absent or trace and mitral valve regurgitation is mild or less.

For the secondary endpoints assessing cardiac valve function and pulmonary arterial pressure listed in Section 5.1.2 the ECHO sub-study data from this study will be pooled with studies ADP356-009, -010, and -011.

#### 8.4.1 Worsened FDA-defined valvulopathy

For subjects with FDA-defined valvulopathy at Baseline, worsened FDA-defined valvulopathy is define as any increase in valvular regurgitation from Baseline in either the aortic or mitral valve.

#### 8.5 CENSORING

The individual EOS date will be defined as the time of the last visit or study contact for each individual patient. If no event occurs for an endpoint, the earlier of the last study contact, the visit following Sponsor Notification of Study Completion or death will be treated as the censoring date.

MACE, MACE+ and conversion to T2DM events will be handled in the following manner according to their timing with respect to study milestones:

- Events that are recorded as beginning prior to the date of randomization will not be counted in the event analyses. The subject will be included in the analysis as not experienced the event. These events that are recorded as beginning prior to the date of randomization they will be included in a listing.
- Events that occur at any time after randomization and up to and including the first of the last visit/contact or visit following Sponsor Notification of Study Completion and reported *before* database lock will be adjudicated and included in all efficacy and safety analyses.
- Events that occur at any time after randomization and up to and including the last visit/contact and reported *after* database lock will be not be adjudicated and will not be included in the primary efficacy and safety analysis. They will be recorded in a tabular fashion as part of the final study report and may be included in sensitivity analyses.
- Events that occur after last visit/contact will not be included in the primary efficacy and safety analyses but may be included in the safety database if they fulfill safety reporting criteria.

Events in subjects who withdraw consent for clinical follow-up:

- All events that occur before withdraw of consent are included in analyses.
- Events that occur after withdraw of consent will be included in the primary analyses if they were found through vital status search prior to database lock.

Events in subjects who stop and re-start study medication.

• For the Total Time Analysis Set all events are counted regardless of whether the subject is on or off treatment.

- For the On-treatment Analysis Set events are counted only when the subject in "on-treatment". See Section 8, for definition of "on-treatment".
- For the On-treatment plus 30 days Analysis Set events are counted when the subject is "on-treatment" and up to 30 days from their last dose. See Section 8, for definition of "on-treatment".

For ITT subjects who were not treated the censoring time will be determined from the randomization date to the date of final disposition.

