9.5.5.2 Discontinuation from Study Procedures/Withdrawal of Consent

A subject may elect to discontinue all participation in the study at any time for any reason. (revised per Amendment 01)

Only subjects who refuse any and all types of contact (eg, visits, telephone calls, medical record reviews) will be considered to have withdrawn consent for all clinical follow-up. It is expected that this would be extremely unusual. The site must contact the TIMI Hotline to confirm withdrawal of consent, at which time the Withdrawal of Consent CRF will be made available for

completion. A final assessment for vital status using publically available data will be performed at the end of the study for all subjects who withdraw consent for all clinical follow-up, when allowed by law, regulation, or local authorities.

The investigator may also withdraw a subject from the study only in the event of exceptional circumstances. This must be documented by the site, signed by the investigator, and reviewed by the sponsor/designee before it is considered to take effect.

All subjects who prematurely discontinue all study procedures (ie, withdraw consent) are to complete the EOS Visit procedures indicated in the schedule of procedures/assessments (Table 4).

For subjects who prematurely discontinue from the study, the reasons will be documented in the CRF and source documentation. Study disposition information will be collected on the Subject Disposition CRF.

A subject removed from the study for any reason may not be replaced.

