## 5.2 STUDY SUBJECTS

#### **5.2.1** Definitions of Analysis Sets

The number (percent) of subjects included in each analysis set will be presented by analysis set, treatment group and overall. The description of the analysis data sets are:

- The Safety Analysis Set: will be the group of subjects who received at least one dose of study drug and had at least one post dose safety assessment.
- The Intent-to-Treat (ITT) Set: will be the group of all randomized subjects regardless of whether they took study drug or not. This is the same as the Full Analysis Set.
- Total Time Analysis Set: Using the ITT, events are counted that occur while subjects are on and off treatment. Subjects with no events will be censored at their last study contact or at the visit following Sponsor Notification of Study Completion, whichever

- occurs first. This analysis set will be used for the primary analysis. See Section 8.5 for censoring algorithm.
- On-Treatment plus 30 Days Analysis Set: Using the ITT, events are counted that occur
  while subjects are "on treatment" and up to 30 days from their last dose. Subjects with
  no events who discontinue early or complete the study will be censored at their last dose
  date plus 30 days. See Section 8 for definition of "on treatment" and Section 8.5 for
  censoring algorithm.
- On-Treatment Analysis Set: Using the ITT, events are counted that occur while subjects are "on treatment". Subjects with no events who discontinue early or complete the study will be censored at their last dose date. See Section 8 for definition of "on treatment" and Section 8.5 for censoring algorithm.
- Prediabetes Analysis Set: This set includes all subjects in the ITT set without a history of any type of diabetes and who are prediabetic at Baseline (defined in Section 8).
- Nondiabetes Analysis Set: This set includes all subjects in the ITT set without a history of any type of diabetes at Baseline (defined in Section 8).
- T2DM Analysis Set: This set will be all subjects in the ITT who have T2DM at Baseline (defined in Section 8).
- FDA-defined Valvulopathy Analysis Set: This set will be all subjects in the ITT without FDA- defined valvulopathy at Baseline (defined in Section 8.4). The data from the ECHO sub-study will be pooled with the ECHO data from the 3 pivotal lorcaserin HCl studies (APD356-009, APD356-010, and APD356-011).

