#### 8.5.2 Censoring at Study Completion

8.5.2.1 Censoring for MACE, MACE+, each Component of MACE, and All-Cause Mortality

If non-inferiority between lorcaserin HCl and placebo is confirmed at the interim analysis, then the study will be continued to observe; 1401MACE+ events at approximately 54 months from the start of the study and 2.5 years median treatment duration.

algorithms

MACE non-inferiority and superiority, each component of MACE, and All-cause mortality will analyzed at study completion as part of additional sensitivity analyses. The censoring algorithm is the same for these endpoints but differs by Analysis Set as described in the Table 6, and see Appendix 13.2 for diagrams of censoring algorithms.

For subjects who experienced an event, their time-to-event will be determined from the randomization date (for the Total Time Analysis) and the start date of study drug (for the On-Treatment and On-Treatment + 30-Days Analyses), to the date of the event. The censoring variable will be, CENSORED=0. For subjects who do not experienced an event, the censoring time will be determined from the randomization date (for the Total Time Analysis) and the start date of study drug (for the On-Treatment and On-Treatment + 30-Days Analyses), to the date described in Table 6, along with a matching censoring variable, CENSORED=1.

Table 6 Censoring Date For subjects who did not experienced an event at Study Completion

Table o Ce	ensoring Date For subjects who did not ex	xperienced an event at Study Completion
Analysis		
Set a	Completed the Study	Withdrawal From Study Follow-up
Total Time	In the Final Study Disposition Form use	In the Final Study Disposition Form use the
on Study	the date from , Date of Final Sponsor	date from , Date of Final Sponsor
	Notification/Premature Study	Notification/Premature Study Discontinuation
	Discontinuation	and
	and status is equal to completed	status for discontinuation equals any of the
		following;
		Withdrew Consent
		Lost to Follow up
		Study Terminated by Sponsor
		• death (except for All Cause-mortality)
		• Other
On-	Date of last dose from Study	Date of last dose from Study Medication Form
Treatment +	Medication Form + 30 Days	+ 30 Days
30 Days		
-		
On-	Date of last dose from Study Medication	Date of last dose from Study Medication Form
Treatment	Form	
a See Section	5.2.1 for definitions of Analysis Sets and A	Appendix 13.5.2 for diagrams of censoring

algorithms

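### After consent withdrawal, SAP 8.5 adds events found by vital-status search but no time at risk for withdrawn subjects found alive; this affects all-cause mortality and, slightly, MACE+ at study completion

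*SAP*

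**What the plan says.** Protocol 9.5.5.2 plans a search covering subjects who withdraw consent for all clinical follow-up, where law allows: "A final assessment for vital status using publically available data will be performed at the end of the study". Such a search can identify the living as well as the dead. The same section reserves withdrawal for subjects who refuse every form of contact, and adds: "It is expected that this would be extremely unusual".

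SAP 8.5 says what to do with the events found: "Events that occur after withdraw of consent will be included in the primary analyses if they were found through vital status search", provided this happens before database lock. Another bullet in SAP 8.5 gives the general rule: "Events that occur after last visit/contact will not be included in the primary efficacy and safety analyses".

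For subjects without an event, SAP 8.5 says that "the earlier of the last study contact, the visit following Sponsor Notification of Study Completion or death will be treated as the censoring date". The Total Time definition in SAP 5.2.1 agrees, except that it does not mention death. SAP Table 6 covers MACE, MACE+, the components of MACE and all-cause mortality. It sends subjects whose status is consent withdrawal to a disposition-form date whose label ends "Notification/Premature Study Discontinuation". No section uses a vital-status or last-known-alive date as a censoring date.

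**The concern.** A withdrawn subject who later has a qualifying death is followed to the death date. A withdrawn subject found alive by the same search is followed only to withdrawal. Whether time after withdrawal enters the risk set thus depends on the outcome, and the Cox model in SAP 5.4 assumes that censoring does not.

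Two things follow. Event rates per 100 patient-years, which SAP 5.4 plans to report, are too high in both arms. The hazard ratio is also pulled away from the truth if more subjects withdraw in one arm than in the other: the arm with more withdrawals looks worse.

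No planned analysis would show this. The multiple imputation in SAP 5.4.1.1 is for subjects lost to follow-up, and the on-treatment sets answer a different question. Nothing applies symmetric censoring to the Total Time set.

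**Working it through.** **The plan's own figures.** Power for MACE+ with 1401 events and HR 0.85: √(1401/4) × |ln 0.85| − 1.96 = 3.04 − 1.96 = 1.08, which gives 86.0% (stated: above 85%). For MACE with 460 events and margin 1.4: √(460/4) × ln 1.4 − 1.96 = 3.61 − 1.96 = 1.65, which gives 95.0% (stated: 95%). Both reproduce, and the point below changes neither.

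**Inputs from the documents.** 12,000 subjects randomized 1:1; 15-month accrual and 54 months in total, so potential follow-up F runs uniformly from 39 to 54 months (3.25 to 4.5 years); MACE+ rate m = 3.5% per year; total drop-out 5% per year.

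**Assumptions, not in the documents.** Constant hazards; all-cause death d = 1.5% per year; CV death c = 0.5% to 1.0% per year; consent withdrawal w = 0.25% to 5% per year; every death after withdrawal is found.

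**All-cause mortality, rule as written.**
- Deaths per subject: E[1 − e^(−dF)].
- Person-years per subject: E[(1 − e^(−dF))/d − F·e^(−dF) + e^(−dF)(1 − e^(−wF))/w].

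For 6,000 subjects in one arm with w = 5%:

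| | Deaths | Person-years | Rate per 100 |
|---|---|---|---|
| All censored at withdrawal | 308.0 | 20,533 | 1.500 |
| Rule as written | 338.7 | 20,574 | 1.646 |

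The rule adds 30.7 deaths on only 41 person-years, which inflates the rate by 9.8%. With w = 1% the rate is 1.529 (+1.9%); with w = 0.25% it is 1.507 (+0.5%). If withdrawn survivors are also followed to the search date, the rate returns to 1.50.

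**MACE+, rule as written.** Before withdrawal:
- Events: m/(m+w) × (1 − e^(−(m+w)F)).
- Person-years: (1 − e^(−(m+w)F))/(m+w).

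After withdrawal only CV deaths are added: ∫₀^F w·e^(−(m+w)s)·[1 − e^(−c(F−s))] ds.

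Per arm with w = 5% and c = 1.0%, the 692.5 events on 19,785 person-years (3.500) become 712.6 events on 19,812 (3.597), +2.8%. With c = 0.5% the rate is 3.549 (+1.4%). With w = 0.25% it is 3.502 to 3.505 (about +0.1%).

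**Hazard ratio, no true effect** (ratio of the two arms' rates, as an approximation to the Cox estimate):

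| Annual withdrawal, placebo vs lorcaserin | Mortality | MACE+ |
|---|---|---|
| 5% vs 5% | 1.000 | 1.000 |
| 5% vs 6% | 1.677/1.646 = 1.018 | 1.003 to 1.006 |
| 5% vs 4% | 1.616/1.646 = 0.982 | 0.994 to 0.997 |

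With a true HR of 0.85 and equal withdrawal, the result stays at 0.850.

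**Type I error.** A log-rank simulation (1,500 replicates, 5% vs 4% withdrawal, nominal one-sided 2.5%, Monte Carlo SE about 0.4 points) gave an error in favour of lorcaserin of 3.6% for MACE+ and 4.6% for mortality. Symmetric censoring gave 2.4% and 2.5%.

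**Why the remedy differs by endpoint.** For mortality, extending survivors restores 1.50 and HR 1.00. For MACE+ it does not, because nonfatal events after withdrawal go unseen: at 5% vs 6% the placebo rate falls to 3.22 to 3.27 and the null HR to 0.984 to 0.987.

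**The case against.** The best answer is that the effect will be too small to matter. The protocol reserves withdrawal for subjects who refuse all contact, requires hotline confirmation, and expects this to be very rare; stopping study drug is not withdrawal. At 0.4% vs 0.6% per year, the lower rate on lorcaserin, the null HR is about 0.996 for mortality and 0.999 to 1.000 for MACE+. Nothing in the documents predicts unequal withdrawal. All-cause mortality is also a secondary endpoint outside the testing hierarchy. This limits the size and stands. It does not make the rule correct.

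A second answer is that dropping known CV deaths from an ITT-based analysis discards ascertained fatal outcomes. That is a fair trade-off for MACE+, so the choice of primary version is left to the sponsor.

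A reader might also infer more than the text supports:

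- *Both primary endpoints are compromised.* MACE is primary only at the interim analysis (SAP 5.1.1), which has its own censoring table (Table 5), and the search comes at the end of the study.
- *Every death after withdrawal extends follow-up.* This is exact only for all-cause mortality. For MACE and MACE+, only CV deaths do so.
- *The hazard ratio could shift by about 4%.* That needs 4% vs 6% withdrawal, treats all drop-out as consent withdrawal, and applies to mortality (1.616/1.677 = 0.964). The same split gives 0.989 to 0.994 for MACE+.
- *The two SAP 8.5 bullets flatly contradict each other.* The withdrawal bullet has its own subheading and reads as an exception to the general rule. What is missing is the cross-reference.

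**Conclusion.** The asymmetry is in the text: after withdrawal, time at risk enters only for subjects with an event. It bears on the analyses at study completion, on all-cause mortality most and on MACE+ slightly.

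Under the assumed rates and withdrawal of 0.25% to 5% per year, the mortality rate is inflated by about 0.5% to 10% and the MACE+ rate by about 0.1% to 3%. The upper ends are bounds, not expectations. Bias in the hazard ratio needs unequal withdrawal; for a 1-point annual difference it is at most about 2% (mortality) or 0.6% (MACE+).

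Three limits apply. The list of handling rules in SAP 8.5 is introduced for MACE, MACE+ and conversion to T2DM, so applying the withdrawal bullet to all-cause mortality is an inference from Table 6, which covers that endpoint. The Table 6 date field carries a double label; SAP 5.2.1 and 8.5 point to last contact. The censoring diagrams in the SAP appendix are not shown and could not be checked.

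**What to change.** 1. **All-cause mortality.** State in SAP 8.5 and Table 6 that every withdrawn subject found alive is censored at the vital-status (last-known-alive) date. Where no search is allowed or status remains unknown, censor at last contact, and report the share of such subjects by arm.
2. **MACE and MACE+ at study completion.** Add an analysis in which events and time at risk end on the same date (withdrawal or last contact). State which of the two versions is primary.
3. **SAP 8.5.** Cross-reference the withdrawal bullet and the bullet on events after last contact, so that the first is an explicit exception to the second. Say whether the withdrawal rule applies to all-cause mortality.

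Cost: a small wording change to SAP 8.5 and Table 6, one extra analysis, and recording an alive date in the search already planned. The documents do not say that the search yields such a date for each survivor, so the search instructions should ask for it.

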## 8.5.1 Censoring at Interim Analysis for MACE

There will be one interim analysis; when 460 adjudicated MACE events have occurred, the primary analysis for MACE will be conducted. The censoring algorithm is found in the Table 5 and see Appendix 13.2 for diagrams of censoring algorithms. See Section 6 for details on interim analysis.

For subjects who experienced an event, their time-to-event will be determined from the randomization date to the date of the event, for the Total Time Analysis. The censoring variable will be, CENSORED=0. For subjects who do not experienced an event, the censoring time will be determined from the randomization date to the date of the data extraction for those continuing in the study or according to the details below for subjects who are not continuing in the study at the time of the interim analysis. For these subjects, the censoring variable will be, CENSORED=1.

Table 5 Censoring Date For subjects who did not experienced an event at the Interim Analysis

Analysis		
Set a	Ongoing	Withdrawal From Study Follow-up
Total Time	Date of the adjudicated CEC database lock will be used for all	In the Final Study Disposition Form use the date from, Date of Final Sponsor Notification/Premature Study
on Study	ongoing subjects	Discontinuation
		and
		status for discontinuation equals any of the following;
		Withdrew Consent
		Non- CV Death
		• Other
a See Section	5.2.1 for definitions of Analysis Set	s and Appendix 13.5.1 for diagrams of censoring

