#### 5.2.2 Subject Disposition

The number of subjects screened and the number (percent) of subjects who failed screening and the reasons for screen failure will be summarized, based on data reported on the Screening Disposition CRF. The distribution of the number of randomized subjects enrolled by each site will be summarized for each randomized treatment group. The primary reasons for screen failures; did not meet inclusion/exclusion criteria, AE, lost to follow-up, withdrawal of consent, and other, will be presented.

For study completion, the number (percent) of randomized subjects who completed the study (e.g. subject was in the study at the date of Final Sponsor Notification/Premature Study Discontinuation by Sponsor, whether subject is on or off treatment or death) and who

discontinued from the study will be summarized according to the primary reason for discontinuation based on data reported on the Final Study Disposition CRF. The number (percent) will be presented by treatment group and total for subjects; randomized, not treated, treated, who completed the study, and discontinued from the study. For those who are considered to have discontinued from the study, the reasons for discontinuation from the study at Final Sponsor Notification/ Premature Study Discontinuation are captured in the Final Study Disposition CRF (Withdrawal of Consent, Lost to follow up, Study prematurely terminated by sponsor, and Other).

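### The SAP gives conflicting censoring dates for the interim MACE non-inferiority test and no rule for subjects lost to follow-up

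*SAP*

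**What the plan says.** SAP 8.5.1 governs censoring at the interim.

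- **Text of 8.5.1.** For event-free subjects, "the censoring time will be determined from the randomization date to the date of the data extraction for those continuing in the study". It continues: "or according to the details below for subjects who are not continuing in the study at the time of the interim analysis".
- **Table 5, ongoing subjects.** "Date of the adjudicated CEC database lock will be used for all" ongoing subjects.
- **Table 5, withdrawal column.** The disposition-form date applies to three statuses: withdrew consent, non-CV death and other.

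SAP 6.1.1 runs the interim on the Total Time analysis population, and the Table 5 footnote sends the reader to SAP 5.2.1 for its definition. That section says: "Subjects with no events will be censored at their last study contact", or at the visit after Sponsor Notification if that is earlier. SAP 8.5 says that, without an event, "the earlier of the last study contact, the visit following Sponsor Notification of Study Completion or death will be treated as the censoring date". Protocol 9.7.1.2 also names last study contact and refers to the SAP for details.

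On later events, SAP 8.5 adds: "Events that occur after last visit/contact will not be included in the primary efficacy and safety analyses". Its stated exception is for events found by a vital-status search in subjects who withdrew consent.

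SAP 5.2.2 lists the reasons for leaving the study as "Withdrawal of Consent, Lost to follow up, Study prematurely terminated by sponsor, and Other". Table 6, the counterpart of Table 5 at study completion, includes "Lost to Follow up". Protocol 9.5.5.2 reserves withdrawal of consent for subjects who refuse every form of contact.

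**The concern.** There are three separate defects in the rule for one analysis.

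1. The text and table of 8.5.1 name different dates for ongoing event-free subjects, and nothing says that extraction and CEC lock fall on the same day.
2. Both dates can fall after last contact, which is the rule stated elsewhere for the same analysis set. Because 8.5 does not count events after last contact, carrying a subject beyond it adds time at risk in which no event can count.
3. A subject who cannot be reached has not withdrawn consent, and other is a different status from lost to follow-up. The text does not say whether such a subject is continuing (carried to extraction or lock) or not continuing (disposition date). One with no discontinuation record may be treated as ongoing.

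At stake is the gatekeeping test. Under SAP 5.3.3 and 6, failing it stops the trial and passing it opens the MACE+ test. Two programmers could follow the SAP and submit different data to it.

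**Working it through.** **The plan's own figure.** With d events, 1:1 allocation and true hazard ratio 1, power = Φ(ln(1.4) × √d / 2 − 1.960). For d = 460: 0.3365 × 10.724 = 3.608; 3.608 − 1.960 = 1.648; Φ(1.648) = 95.0%. This matches SAP section 4. The censoring question changes neither the event target nor the nominal alpha.

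**Inputs from SAP 3.3 and 4.** 12,000 subjects 1:1, 15-month accrual, placebo MACE rate 1.5% per year, margin 1.4, one-sided 0.025, analysis at the 460th event.

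**Assumed, because the documents do not give them.** Loss rates by arm (constant hazards κ, unrelated to events), uniform accrual, every lost subject carried to lock, no event found after loss, unstratified Cox model.

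**Method.** Let λ be the arm's event hazard and G(t) the share of subjects randomized early enough to have t years of follow-up.

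- Observed event density: λ·exp(−(λ+κ)t)
- Share at risk if censored at last contact: exp(−(λ+κ)t)
- Share at risk if carried to lock: S(t) = 1 − [λ/(λ+κ)]·[1 − exp(−(λ+κ)t)]

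The large-sample Cox estimate b solves ∫G·[d₁ − (d₀+d₁)·eᵇS₁/(S₀+eᵇS₁)]dt = 0, where d is the event density and 0 and 1 denote placebo and lorcaserin. The unobserved share of person-time in an arm is 1 − ∫G·exp(−(λ+κ)t)dt / ∫G·S dt.

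**Results at true hazard ratio 1.4** (460th event at about month 34 to 35):

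| Loss per year, placebo / lorcaserin | Unobserved person-time, placebo / lorcaserin | HR, carried to lock | False non-inferiority | 3,000 simulated trials: HR, false non-inferiority |
|---|---|---|---|---|
| 3% / 3% | 3.4% / 3.4% | 1.40 | 2.5% | 1.40, 2.4% |
| 1% / 2% | 1.1% / 2.3% | 1.38 | 3.3% | 1.39, 3.5% |
| 2% / 4% | 2.3% / 4.5% | 1.37 | 4.3% | 1.37, 4.4% |
| 3% / 7% | 3.5% / 7.9% | 1.34 | 7.2% | 1.34, 7.0% |
| 4% / 2% | 4.5% / 2.3% | 1.43 | 1.4% | 1.43, 1.5% |

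Monte Carlo error is at most about ±0.9 points. Censoring at last contact gives 1.40 and 2.5% in every row by the formula, and 2.5% to 2.7% in the same simulated trials.

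**Hand check of the 2% / 4% row.** The hazard ratio shrinks by the ratio of observed shares: 1.4 × (1 − 0.045)/(1 − 0.023) = 1.368. Then ln(1.4/1.368) × 10.724 − 1.960 = 0.248 − 1.960 = −1.712, and Φ(−1.712) = 4.3%.

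**True hazard ratio 1.0.** Power is 95.0% with last-contact censoring. It falls to 91.2% when 4% (placebo) and 2% (lorcaserin) are lost per year and carried to lock.

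**Extraction against lock.** Moving the censoring date of every ongoing event-free subject 14 to 90 days past the event cut-off leaves the hazard ratio at 1.40, the error at 2.5% and power at 95.0%. The choice between these two dates does no measurable harm by itself; the harm comes from time after last contact.

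**The case against.** Section 8.5.1 is the specific interim rule, and 5.2.1 defers to section 8.5 for the algorithm. The general rule in 8.5 is tied partly to Sponsor Notification, which has not happened at the interim. So 8.5.1 may be meant to override it, with Table 5 as the algorithm. That reading is possible, but the SAP does not state it. It would still leave the text and table of 8.5.1 naming different dates, and it would still count time after last contact.

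The quantified harm also rests on a worst case. If only half of lost subjects are carried to lock, false non-inferiority is 2.9% at 1% / 2%, 3.4% at 2% / 4% and 4.6% at 3% / 7%. If one fifth are carried, it is 2.7%, 2.8% and 3.2%. Patient finder services, vital-status efforts, telephone visits and the retention plan should keep the group small. This stands, and it limits the likely size.

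The censoring diagrams to which 8.5.1 refers are not visible in the text reviewed. They may settle how a lost subject is handled, but they would not remove the contradiction in the written rules.

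Finally, last-contact censoring looks perfect here partly because the model assumes continuous contact until a loss unrelated to events. Real visits are months apart, and an event itself can prompt a contact. That is a fair limit on the comparison. Last contact is nonetheless the SAP's own rule.

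**Conclusion.** The concern holds and should be fixed. All three defects are in the text: two dates within 8.5.1, both at odds with the last-contact rule for the same analysis set, and no lost-to-follow-up status in Table 5.

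The size is conditional. Equal loss between arms produces no material bias. More loss on lorcaserin pulls the hazard ratio down and makes false non-inferiority more likely; more loss on placebo pushes it up and costs power. Over the assumed loss rates, with every lost subject carried to lock, false non-inferiority ranges from 1.4% to 7.2% against a nominal 2.5%. These figures are illustrations, since loss by arm is not in the documents. Confidence in the contradiction is high, but the effect on the actual interim result cannot be determined from the documents. The repeat of MACE non-inferiority at study completion (SAP 5.4.1.1) could expose a distorted interim result but could not undo the decision to continue or stop.

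**What to change.** Write one rule and use it in both the text and Table 5 of 8.5.1:

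- Censor each event-free subject at the earliest of the last contact at which endpoint status was ascertained (any contact, not only a scheduled visit), non-CV death, or one named interim data cut-off date.
- Count events only up to the same cut-off.
- Add lost to follow-up to Table 5, censored at last contact, and state the same last-contact date in Table 6.
- Align 5.2.1 and 8.5 with this wording.

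The SAP reviewed is V3.0 of 18 May 2018, and the interim was expected by about July 2017. If it has been run, state which date was used, report unobserved person-time by arm, and repeat the interim Cox model with last-contact censoring as a sensitivity analysis.

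The cost is SAP wording and one derivation, plus one model rerun if the interim is done. No new data should be needed.
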